8.5.2 Collection, Recording and Reporting of Serious Adverse Events

SAE Reporting by the Investigator

All SAEs must be reported **immediately** to Ferring Pharmacovigilance as soon as it becomes known to the investigator and not later than within 24 hours of their knowledge of the occurrence of an SAE.

The investigator is responsible for submitting the completed SAE Report Form with the fullest possible details **within 3 calendar days** of his/her knowledge of the SAE.

The SAE Report Form is included in the e-CRF system, and must be completed and submitted according to the instructions provided on the form. In case the e-CRF cannot be accessed and hence the SAE Report Form cannot be filled in within the e-CRF system, a paper SAE Report Form should be used and sent to Ferring Pharmacovigilance using the contact details below.

Ferring Pharmacovigilance
E-mail: [REDACTED]
Fax: [REDACTED]

Completion of the Demographics, Adverse Event Log, Medical History Log and Concomitant Medication Log are mandatory for initial reports and for follow-up reports if any relevant changes have been made since the initial report. Data entries must have been made in the e-CRF for Ferring Pharmacovigilance to access the information.

Additional information relevant to the SAE such as hospital records, results from investigations, e.g., laboratory parameters (that are not already uploaded in the e-CRF), invasive procedures, scans and X-rays and autopsy results can be faxed or scanned and e-mailed to Ferring Pharmacovigilance using the contact details in the section above. In any case this information must be supplied by the investigator upon request from Ferring. On any copies provided, details such as maternal subject's name, address and hospital ID number should be concealed and instead maternal subject number should be provided.

The investigator will supply Ferring and the IRBs with any additional requested information such as results of post-mortem examinations and hospital records.

Ferring will report all SAEs according to local regulations.

8.6 Follow-up of Adverse Events and Serious Adverse Events

8.6.1 Follow-up of Adverse Events with Onset during the Trial

During the trial, the investigator must follow-up on each AE, maternal or infant, until it is resolved or until the medical condition is stable.

After the Day 18/Follow-up visit, the investigator must follow-up on any AE classified as serious or considered to have a reasonable possible causality to the IMP until it is resolved or until the medical condition is stable. All such relevant follow-up information must be reported to Ferring. If the event is a chronic condition, the investigator and Ferring may agree that further follow-up is not required.

8.6.2 Collection of Serious Adverse Events with Onset after Last Trial Visit

If an investigator becomes aware of an SAE of the maternal subject after the Day 18/Follow-up visit, and he/she assesses the SAE to have a reasonable possible causality to the IMP, the case will have to be reported to Ferring, regardless of how long after the end of the trial this takes place.

If an investigator is informed of a hospital re-admission of the infant from the follow-up call about one month after infant' discharge from NICU, and he/she assesses the reason for the re-admission to have a reasonable possible causality to the IMP, the case will be reported as an SAE to Ferring. Similarly, if an investigator becomes aware of an SAE of the infant during the infant's long-term follow-up, and he/she assesses the SAE to have a reasonable possible causality to the IMP, the case will have to be reported to Ferring. The SAE will be followed up until the event is resolved or until the medical condition is stable.

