1.2 Scientific Justification for Conducting the Trial

The initial clinical development of merotocin was a combined single ascending and multiple ascending dose phase 1 trial to assess safety, tolerability and pharmacokinetics (PK) of merotocin in healthy non-lactating women. No safety or tolerability concerns were raised in that trial with doses up to 400 µg intra-nasally every 3 hours for 45 hours.¹⁹

Subsequently, the transfer of merotocin from blood to breast milk was investigated in a single-dose milk transfer trial in healthy women with full-term delivery. In that trial, merotocin was administered as an intravenous dose of 20 µg equivalent to 400 µg intra-nasally. For all subjects, the concentration of merotocin in the milk was below the lower limit of quantification.¹⁹ The infants of maternal subjects exposed to merotocin in this trial can therefore be fed with MoM with no expectation that the infants will be exposed to the drug.

A proportion of mothers with preterm birth that are dependent on a breast pump have difficulty establishing adequate milk supply to meet their infants' nutritional needs. A product to enhance lactation so that prematurely born infants to a higher degree can be nourished with MoM would address a medical need. The current trial is the first investigation in the target population of women with preterm delivery and inadequate initial milk production who are generally breast pump dependent. The primary objective of the trial is to explore the efficacy of intra-nasally administered merotocin in increasing milk production in the target population and thereby to provide efficacy information for the planning of future trials. In the current trial, merotocin will be administered as a nasal spray. This is a common mode of administration for peptidic products in order to avoid the enzymatic degradation that would occur with oral administration and the subsequent low bioavailability.

Further objectives of the trial are to obtain information on safety in the maternal subjects and their infants when infants are fed with MoM from maternal subjects exposed to merotocin.

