7.4 Assessments Related to Post-trial Endpoints

Additional data will be collected from the hospital records of the infant when the infant is discharged from NICU. The additional data (if available) are infant body weight, length and head circumference at time of infant's discharge from NICU, the date when the infant becomes tolerant to full enteral feeding, date of discharge from NICU, number of days the infant requires TPN until discharge from NICU, type of feeding (MoM and formula/donor milk) at time of infant's discharge from NICU, and whether the maternal subject is lactating (i.e., breastfeeding or breast pumping) at time of infant's discharge from NICU.

Concomitant medications and AEs will be collected from hospital records through time of infant's discharge from NICU or until the last milk sample expressed during maternal subject's treatment with IMP is either consumed by the infant or discarded, whichever occurs last. Information on infant's morbidity events of special interest occurring prior to the infant's discharge from NICU, including NEC, intra-ventricular hemorrhage, BPD, RDS, late-onset sepsis, ROP, and hemodynamically significant patent *ductus arteriosus*, are recorded at the time of infant's discharge from NICU based on hospital records. The trial is not powered to draw conclusions on the incidences of these events, but they are collected in order to capture any trends on the impact of feeding patterns on their incidences.

From the follow-up contact about one month after the infant's NICU discharge, the date of any hospital re-admission of the infant occurring since NICU discharge, and the reason for the re-admission will be recorded. Investigators should assess the causal relationship between the reason for such re-admissions and the IMP.

For long-term follow-up, the ASQ-3 will be provided for all infants at 9 months, 18 months and 24 months of corrected gestational age. A primary caregiver of the infant will answer the questionnaire that consists of approximately 30 questions covering five domains of development, including communication, gross motor, fine motor, problem-solving, and personal-social skills. It takes about 15-30 minutes to complete the questionnaire. If a score falls into the black zone of any domain on the scoring summary sheet, standard referral procedures should be followed.

Data from post-trial activities will be provided in an addendum to the clinical trial report.

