Reasonable possibility: There is evidence or argument to suggest a causal relationship between the IMP and the AE. The AE may occur as part of the pharmacological action of the IMP or may be unpredictable in its occurrence

Examples:

- AEs that are uncommon but are known to be strongly associated with IMP exposure
- AEs that are not commonly associated with IMP exposure, but the event occurs in association with other factors strongly suggesting causation, such as a strong temporal association with the IMP or the event recurs on rechallenge with the IMP

No reasonable possibility: There is no reasonable evidence or argument to suggest a causal relationship between the IMP and the AE

Examples:

- Known consequences of the underlying disease or condition under investigation
- AEs common in the trial population, which are also anticipated to occur with some frequency during the course of the trial, regardless of IMP exposure

Action Taken to IMP

The action taken to the IMP in response to an AE must be classified as one of the following:

- No change (medication schedule maintained or no action taken)
- Discontinued
- Interrupted
- Dose reduced

Other Action Taken

AEs requiring therapy must be treated with recognized standards of medical care to protect the health and well-being of the maternal subject.

If medication is administered to treat the AE, this medication should be entered in the Concomitant Medication Log. Infant concomitant medication needs to be reported in the electronic system only once (dose and frequency may be omitted), as a complete list of medications (including dose and frequency, as applicable) may be printed from the hospital records (de-identified) and sent to the sponsor following discharge of the infant from the NICU if more information is later needed.

Date and Time of Outcome

The date and time the subject recovered or died.

Outcome

The outcome of an AE must be classified as one of the following:

- Recovered (fully recovered or the condition has returned to the level observed at initiation of trial treatment)
- Recovered with sequelae (resulted in persistent or significant disability/incapacity)
- Recovering
- Not yet recovered
- Fatal

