8.2.4 Collection and Recording of Adverse Events for Infants

Events that occur in infants following the signing of parental consent are to be collected as AEs. Data regarding these AEs are to be recorded in the e-CRF using information obtained from the infant's hospital records (as available). Infant AEs will be collected and recorded from the time informed consent is obtained through the Day 18/Follow-up visit during the trial. As part of post-trial activities after the Day18/Follow-up visit, infant AEs will also be collected and recorded through time of infant's discharge from NICU or until the last milk sample expressed during maternal subject's treatment with IMP is either consumed by the infant or discarded, whichever occurs last. These AEs will be reported separately from those collected through the Day 18/Follow-up visit.

About one month after the infant's NICU discharge, the maternal subject will be contacted (by phone or other means) to inquire about any hospital re-admission and the reason for such.

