9.6.5 Post-trial Endpoints

Post-trial endpoints will be presented in summary tables.

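### Section 8.6.2 makes SAE reporting of an infant re-admission depend on causal attribution, with no exception for infants whose AE window under Section 8.2.4 is still open

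*Combined protocol and SAP*

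**What the plan says.** Section 8.2.4 collects infant AEs through the Day 18 visit. After that, collection runs to NICU discharge or until the last milk expressed on treatment "is either consumed by the infant or discarded, whichever occurs last". Footnote e of Table 4 repeats this. Section 8.1 treats infant AEs as treatment-emergent from first to last exposure to that milk. Section 8.5.1 counts an in-patient admission of at least 24 hours as serious. It also asks for fatal outcomes to be reported, including those up to 4 weeks after treatment, whatever the causal relationship. Section 8.5.2 requires all SAEs to be reported at once and "not later than within 24 hours of their knowledge of the occurrence".

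Section 8.6.2 differs. If a re-admission is learned of at the one-month contact and "he/she assesses the reason for the re-admission to have a reasonable possible causality to the IMP, the case will be reported as an SAE", the case goes to the sponsor. The same condition applies "if an investigator becomes aware of an SAE of the infant during the infant's long-term follow-up".

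Independently of causality, Section 7.4 records "the date of any hospital re-admission of the infant occurring since NICU discharge", together with the reason. Re-admission is not among the post-trial endpoints in Section 2.2. On analysis, Section 9.6.5 says only: "Post-trial endpoints will be presented in summary tables". Section 9 announces a separate SAP for the post-trial information; it is not among the documents.

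**The concern.** The infant AE window can outlast NICU discharge, because it follows the milk and not the hospital stay. Section 8.6.2 is written as if the window had always closed by then. A site that follows it will not submit an SAE for an in-window re-admission that it judges unrelated, although four other sections call for one.

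This matters because infant safety is a secondary objective and this is the first trial in the target population. Individual attribution is also a weak screen here. Section 1.2 says that infants can be fed "with no expectation that the infants will be exposed to the drug", and Section 8.2.2 gives "AEs common in the trial population, which are also anticipated to occur with some frequency" as an example of no reasonable possibility. Both make a judgement of unrelated more likely. If sites resolve the conflict differently, the treatment-emergent infant SAE table depends partly on which section each site followed.

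**Working it through.** No figure in the plan bears on this point, so the check is a comparison of text, followed by two illustrations on stated assumptions.

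**1. When the window is open after discharge.** Once NICU discharge and the Day 18 visit have both passed, Section 8.2.4 stays open only while treatment-period milk remains to be consumed or discarded. Section 8.1 ends the infant treatment-emergent interval at that same point. For an infant who has been fed any of this milk, an event in this late part of the window is therefore also treatment-emergent.

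**2. The rules applied to one case.** Take an infant at home after the Day 18 visit, still fed stored treatment-period milk, and admitted for more than 24 hours for a cause judged unrelated.

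| Section | Causality condition | Consequence |
|---|---|---|
| 8.2.4, Table 4 footnote e | None | AE is recorded |
| 8.1 | None | Treatment-emergent |
| 8.5.1 | None | Serious |
| 8.5.2 | None | Reported within 24 hours |
| 8.6.2 | Yes | No SAE report called for |

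**3. Which rule prevails.** The text does not say. Section 8.6.2 is headed as covering onset after the last trial visit, the definitions in Section 8.5.1 are headed as covering SAEs during the trial, and Section 14.3 ends the trial at the last subject's Day 18 visit. A site could reasonably take Section 8.6.2 as governing everything after Day 18. The re-admission sentence itself has no onset limit: the contact covers all time since NICU discharge, which can precede Day 18.

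**4. Whether another route catches the event.** Infant AEs come from hospital records as available (Section 8.2.4). The last AE entry in Table 4 is at NICU discharge. The one-month contact asks only about re-admission and its reason (Section 6.6.2). An admission elsewhere may therefore come to light only there.

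**5. Deaths.** A re-admission ending in death within 4 weeks after treatment is reportable irrespective of causality under Section 8.5.1. Section 8.6.2 makes the re-admission conditional and does not mention this clause.

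**6. How long the window might last (illustration).** From the protocol: full feed of 150 mL/kg/day, volume targets of 500 and 750 mL/day, and 14 treatment days. Assumed: infant weights of 1.5 and 2.0 kg, full feeds throughout, and only stored milk fed after Day 14. With mean production P and weight w:

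extra days after Day 14 = (P − 150w) × 14 / (150w)

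- P = 300, w = 2.0: (300 − 300) × 14 / 300 = 0
- P = 350, w = 2.0: (350 − 300) × 14 / 300 = 2.3
- P = 350, w = 1.5: (350 − 225) × 14 / 225 = 7.8
- P = 500, w = 2.0: (500 − 300) × 14 / 300 = 9.3
- P = 500, w = 1.5: (500 − 225) × 14 / 225 = 17.1
- P = 750, w = 1.5: (750 − 225) × 14 / 225 = 32.7

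A constant 500 mL/day is optimistic, since mothers enter below 200 mL/day; a linear rise from 200 to 500 averages (200 + 500) / 2 = 350. Lower early feeds, or mixing in fresh milk, would lengthen the window. Discarding milk would shorten it.

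**7. Precision of a table by arm (illustration).** With 50 infants per arm and an assumed re-admission rate p, SE = √(2p(1 − p)/50). At 10% this is 6.0 percentage points, and at 15% it is 7.1. The 95% half-widths are 1.96 × 6.0 = 11.8 and 1.96 × 7.1 = 13.9 points.

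**The case against.** The strongest reply is that the plan already covers these events. While the window is open, Sections 8.2.4, 8.5.1 and 8.5.2 apply in full. Section 9.6.3 summarises all infant AEs by treatment group, and Section 9.8.2 tabulates infant TEAEs and lists a treatment-emergent SAE table. Section 8.6.1 requires follow-up after Day 18 of any serious AE, related or not. Section 8.6.2 never says that only attributed cases are reported, and it does not repeal the other sections. On this reading, what is missing is a cross-reference.

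Much of that stands, and it rules out two stronger readings. A reader might infer that after NICU discharge serious infant events count only if attributed to the IMP; inside the window the documents require the opposite, so the defect there is an unresolved conflict. A reader might also infer that a later infant death is reportable only if judged causal; the 4-week clause in Section 8.5.1 contradicts this, and 28 days covers every illustrated window except the 32.7-day extreme.

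The reply does not dispose of the conflict itself. Section 8.6.2 is the passage a site will consult at the one-month contact. It states a condition without the exception that the other sections need, and that contact may be the only place where the event is seen.

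**Conclusion.** The point holds as a conflict in the SAE rules that can bias treatment-emergent infant SAE counts downward. It rests on the text alone. The size cannot be derived: the documents give no re-admission rate, no rate of related judgements and no milk-storage pattern. The illustrated window runs from 0 to about 33 days after Day 14, and from 2 to 8 days at a mean of 350 mL/day, so few infants may be affected. Early discharge is nevertheless foreseen in Sections 3.1.2 and 6.4.3, and the upper gestational age was raised to 34 weeks + 2 days (Section 3.6.6).

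A reader might infer that no unfiltered comparison of re-admissions between arms is possible. The documents do not support that. Section 7.4 records every re-admission reported at the contact, with its date and reason, and the separate post-trial SAP could tabulate them. What can be said is that this protocol does not specify such a table. Nor do the documents support the inference that attribution would remove nearly all events, since no proportion is given.

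**What to change.** Reconcile Section 8.6.2 with Sections 8.2.4, 8.5.1 and 8.5.2. State that an infant re-admission meeting the seriousness definition, or any other infant SAE, with onset while the Section 8.2.4 window is open is recorded and reported as an SAE irrespective of causality, however the investigator learns of it. It should enter the infant treatment-emergent tables when onset falls in the Section 8.1 exposure interval; for onset after Day 18, that means the separately reported set that Section 8.2.4 already prescribes. The causality condition would then apply only after the window closes, and the 4-week clause on deaths should be cross-referenced. To apply this rule, the site needs the date on which the last treatment-period milk was consumed or discarded, so the one-month contact should confirm it.

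In addition, have the separate post-trial SAP include one descriptive table by arm of all infant re-admissions (infants, events, reasons) and known deaths up to the one-month contact, irrespective of causality. The re-admission data are already collected under Section 7.4.

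The cost is protocol wording, a few more SAE forms and one table. At about 50 infants per arm the table can only describe.

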9 STATISTICAL METHODS

The Ferring Global Biometrics Department will be responsible for the statistical analyses of the primary, secondary and exploratory endpoints. This section details the planned statistical analyses for the primary endpoint and outlines the planned statistical analyses for the secondary and exploratory endpoints. All analyses and further descriptions of the statistical methodology for the primary, secondary and exploratory endpoints will be included in the Statistical Analysis Plan (SAP) available before breaking the blind of the trial. A separate SAP will be prepared to cover the post-trial information.

9.1 Determination of Sample Size

The primary objective of this trial is to evaluate the effect of merotocin on increasing milk production in women with preterm delivery. The comparison is based on the primary endpoint of the volume of MoM produced over Days 1 to 14.

Since neither the onset nor the duration of effect of merotocin is known, the initial sample size calculation is based on a comparison of the time-averaged difference between the merotocin group and the placebo group over Days 1 to 14. A sample size of 100 maternal subjects, allocated equally to each treatment group, will provide roughly 80% power to detect a 50% increase in the volume of MoM produced over Days 1 to 14, compared to placebo.

The primary analysis of the volume of MoM obtained over Days 1 to 14 will be based on a repeated measures ANCOVA. For a given sample size, the power is a function of the assumed (constant) treatment effect and the assumed correlation of observations within subjects. The power for a sample size of 100 maternal subjects equally distributed between the two treatment groups for various combinations of correlation and treatment effect is shown in [Table 7](#). As shown in the table, a sample size of 100 subjects has approximately 80% power to detect a 50% increase in the volume of MoM produced, unless the within subject correlation is greater than 0.8.

Table 7 Power for Various Combinations of Correlation and Treatment Effect

Correlation	Treatment effect ^a (merotocin relative to placebo)		
	30% increase	40% increase	50% increase
0.6	64.2 %	81.1 %	92.3 %
0.7	57.2 %	74.4 %	86.1 %
0.8	52.1 %	66.5 %	80.2 %

^a Assuming 100 subjects will be equally distributed between the two groups, with a uniform 30% drop-out rate in the trial.

The results presented in [Table 7](#) are based on simulations. For each scenario, 1,000 datasets with 100 subjects equally distributed between the 2 treatment groups were generated. In each simulation, 14 observations from a multivariate log-normal distribution were generated for each subject. The means and variances of the multivariate log-normal distribution used to draw samples from, were based on external data received by Ferring. The correlation between the volume of MoM expressed

on any two given days by the same individual was assumed to be constant and is provided in [Table 7](#) for each scenario. To account for subjects not completing the trial, a 30% drop-out rate over the duration of the trial was built into each simulation. It is estimated that approximately 250 maternal subjects will need to be screened.

